#### 10.2.2. Baseline Evaluations

Demographic information and baseline disease characteristic data collected in the parent study will be summarized. Data to be tabulated will include sex, age, and race, as well as disease-specific information.

#### 10.2.3. Efficacy Analyses

Associations between PD (serum TTR) and efficacy data will be explored via correlation.

Summary statistics of observed values and changes from baseline will be provided for the mNIS +7 composite score. Summaries will also be provided for the components of the composite score (ie, the NIS weakness and reflex scores, the  $\Sigma$ 5 NCS, and QST values). The NIS+7 score (including full NIS, NCS, VDT, and HRdb), and full NIS will be summarized also.

Patient reported quality of life and disease burden will be assessed by summary statistics for the EQ5D and R-ODS. Summary statistics will be provided for observed values and changes from baseline. Patient reported autonomic neuropathy symptoms will be assessed by descriptive statistics for the COMPASS 31.

Descriptive statistics will also be provided for observed values and changes from baseline in motor function (10-meter walk test and test of grip strength), nutritional status (mBMI), sensory

and autonomic innervation (IENFD and SGNFD), VDT, and ambulation (FAP stage and PND score).

Summary tables and graphical displays of observed values and changes from baseline in serum TTR will be used to assess the durability of suppression over the course of the study.

Descriptive statistics will be provided for actual values and changes from baseline in serum levels of troponin I and NT-proBNP in the subset of patients with evidence of pre-existing cardiac amyloid involvement. Results of echocardiograms will be summarized.

#### **10.2.4. Safety Analyses**

A summary of exposure to patisiran, including the durations of the infusions and doses, and the proportions of patients with modifications in the durations of infusions will be produced.

Adverse events will be summarized by the Medical Dictionary for Regulatory Activities (MedDRA) system organ class and preferred term. Separate tabulations will be produced for all treatment emergent AEs, treatment-related AEs (those considered by the Investigator as at least possibly drug related), SAEs, and discontinuations due to AEs, and AEs by severity. By-patient listings will be provided for deaths, SAEs, and events leading to discontinuation of treatment.

Descriptive statistics will be provided for clinical laboratory data and vital signs data, presented as both actual values and changes from baseline relative to each on-study evaluation and to the last evaluation on study. Laboratory shift tables from baseline to worst values will be presented.

#### **10.2.5. Healthcare Utilization Assessments**

A listing of healthcare utilization data will be presented.

#### **10.2.6. Interim Analysis**

Interim data examinations may be performed, but these will be of a descriptive nature and will not involve any formal hypothesis testing.

## **11. DIRECT ACCESS TO SOURCE DATA/DOCUMENTS**

### **11.1. Study Monitoring**

The Clinical Monitor, as a representative of the Sponsor, has an obligation to follow the study closely. In doing so, the Monitor will visit the Investigators and sites periodically and maintain frequent telephone and written contact. The Monitor will maintain current personal knowledge of the study through observation, review of study records and source documentation and discussion of the conduct of the study with the Investigator and staff.

All aspects of the study will be carefully monitored by the Sponsor or its designee for compliance with applicable government regulations in respect to Good Clinical Practice (GCP) and current standard operating procedures.

### **11.2. Audits and Inspections**

The Investigator and the site will permit study-related monitoring, audits and review by the IEC or IRB and/or Regulatory Authorities, providing direct access to source data/documents. The study may be subject to audit by the Sponsor or its representatives or by regulatory authorities. If such an audit occurs, the Investigator must agree to allow access to the required patient records. In the event of an audit, the Investigator agrees to allow the Sponsor, representatives from the Sponsor, or regulatory agencies access to all study records.

### **11.3. Institutional Review Board**

The Investigator must obtain IRB or IEC approval for the investigation. Initial IRB approval, and all materials approved by the IRB for this study including the patient consent form and recruitment materials must be maintained by the Investigator and made available for inspection.

## 12. QUALITY CONTROL AND QUALITY ASSURANCE

Study personnel are expected to adhere to the following practices, governed by GCP and all applicable regulatory requirements. To ensure these practices are in place, the Sponsor may conduct a quality assurance audit.

The Investigator will submit reports of SAEs as outlined in this protocol. In addition, the Investigator agrees to submit progress reports to his/her IRB or IEC per their local reporting requirements, or at least annually and at the conclusion of the study. The reports will be made available to the Sponsor or designee.

Deviations from the protocol necessary to protect patient safety should be reported to the CRO within 24 hours of knowledge of the event.

Any communications from regulatory agencies in regard to inspections, other studies that impact this protocol or the qualifications of study personnel should be promptly reported to the CRO.

Major changes in this research activity, except those to remove an apparent immediate hazard to the patient, must be reviewed and approved by the Sponsor and the IRB or IEC that approved the study. Amendments to the protocol must be submitted in writing to the Investigator's IRB or IEC and the Regulatory Authority for approval before patients are enrolled under the amended protocol.

Regulatory authorities will receive the protocol, amendments, reports on SAEs, and the Integrated Clinical Trial Report according to national and any local regulations.

## **13. ETHICS**

### **13.1. Ethics Review**

National regulations and International Conference on Harmonization (ICH) require that approval be obtained from an IRB or an IEC prior to participation of patients in research studies. Prior to the study onset, the protocol, any protocol amendments, informed consent forms (ICFs), and any other written information regarding this study to be provided to a patient or patient's legal guardian must be approved by the IRB or IEC.

All IRB and IEC approvals must be dated and contain IRB/IEC Chairman or designee authorization and must identify the IRB/IEC (eg, name and address), the clinical protocol by title and/or protocol number, and the date of approval or favorable opinion was granted for the clinical research.

The Investigator should not start any study procedure with the patient until documentation of the approval by the IEC/IRB and written notification of the approval from the head of the study site to the Investigator and Alnylam Pharmaceuticals, Inc.

No drug will be released to the site to dose a patient until written IRB/IEC authorization has been received by the Sponsor or designee.

The Investigator is responsible for obtaining continuing review of the clinical research at least annually or more often if specified by the IRB or IEC. The Investigator must supply the Sponsor with written documentation of the approval of the continued clinical research.

The Investigator will make all attempts to ensure that the IRB or IEC is constituted and operates in accordance with Federal and ICH GCP and any local regulations.

### **13.2. Ethical Conduct of the Study**

This study will be performed in accordance with the clinical trial agreement, the protocol, all applicable government laws, regulations, and guidances where the study is being conducted including policies with foundations in the World Medical Association Declaration of Helsinki, the ICH of Technical Requirements for Registration of Pharmaceuticals for Human Use, the Health Insurance Portability and Accountability Act of 1996 (HIPAA) in the US, and all other applicable medical privacy laws and regulations.

#### **13.2.1. Financial Disclosure Reporting Obligations**

Each Investigator (including Principal and any Sub Investigators) directly involved in the treatment or evaluation of study patients is required to provide financial disclosure information according to all applicable legal requirements. In addition, Investigators must commit to promptly updating this information if any relevant changes occur during the study and for a period of one year after the completion of the study.

### **13.3. Written Informed Consent**

Written informed consent in compliance with 21 Code of Federal Regulations (CFR) § 50 and ICH will be obtained from each patient before undergoing any protocol-specific tests or procedures that are not part of routine care.

The Sponsor or the CRO designee will provide an ICF template to the Investigator for use in developing a site-specific ICF. Prior to submission of the site-specific ICF to the IRB or IEC, the site-specific ICF must be reviewed and approved by the Sponsor or designee. Any changes requested by the IRB or IEC must also be agreed upon. The final IRB/IEC approved ICF must be provided to the Sponsor. Revisions to the ICF required during the study must be agreed upon, and a copy of the revised ICF provided to the Sponsor.

At the time of recruitment, each prospective patient (or legal guardian) will be given a full explanation of the study and be allowed to read the ICF. Once the Investigator is assured that the patient/legal guardian understands the commitments of participating in the study, the patient/legal guardian will be asked to sign and date the ICF. A copy of the fully signed and dated ICF will be given to the patient. The original ICF will be maintained in the patient's medical record at the site. All active patients will sign an updated ICF if revisions are made to the ICF during the course of the study.

Prior to dosing in this study, the patient will sign and date the ICF and receive a copy of the signed ICF. No study procedures should be performed before informed consent is obtained. The Investigator or another person authorized by the Investigator will also sign and date the informed consent before giving a copy to the patient. The ICF will be filed in the patient's medical record.

### **13.4. Compensation for Health Damages**

A copy of the certificate of insurance as a measure to compensation for health damages will be submitted to the IRB/IEC if required per local regulations.

## **14. DATA HANDLING AND RECORD KEEPING**

### **14.1. Case Report Forms**

The Investigator and designees agree to maintain accurate CRFs and source documentation as part of these case histories. Source documents are the originals of any documents used by the Investigator or hospital/institution that allow verification of the existence of the patient and substantiate the integrity of the data collected during the trial.

The Sponsor will supply CRFs for each patient. Case report forms must be completed only by persons designated by the Investigator. Corrections must be made so as not to obliterate original data and must be identified and dated by the person who made the correction. All data entered into the CRF must also be available in the source documents. The Investigator will allow designated Sponsor representatives and regulatory bodies to have direct access to the source documents to verify the data reported in the CRFs.

Each completed CRF must be reviewed and signed by the Investigator or designee in a timely manner. The completed CRF will be the records maintained by the Sponsor. A copy of the CRF will remain in the Investigator's files.

### **14.2. Confidentiality**

The Investigator must ensure that the patients' anonymity will be maintained. On the CRFs or other documents submitted to the Sponsor or designees, patients should not be identified by their names, but by the assigned patient number and initials. If patient names are included on copies of documents submitted to the Sponsor or designees, the names (except for initials) will be obliterated and the assigned patient number added to the document. Documents not for submission to the Sponsor (eg, signed ICFs) should be maintained by the Investigator in strict confidence.

Following the principles of the GCP, if local regulations specify a patient's number and initials will be used to identify the patient on their study records. Laboratory samples may be labeled with an independent numbering code, and the label will not contain any other personal identification information. The numbering code associated with these labels will be held by the study CRO and the Sponsor, thereby allowing no unwarranted access to the information. The numbering code will also be held for samples in storage until marketing approval of patisiran in the countries where this study was conducted, or until clinical development of patisiran is halted. Throughout sample collection, storage (limited, staff only access area containing locked sample storage, and limited access sample tracking) and processing, the samples will only be handled by appropriate personnel per the laboratory's standard operating procedures.

The Investigator must treat all of the information related to the study and the compiled data as confidential, whose use is for the purpose of conducting the study. The Sponsor must approve any transfer of information not directly involved in the study.

### **14.3. Inspection of Records**

The Sponsor will be allowed to conduct site visits to the investigation facilities for the purpose of monitoring any aspect of the study. The Investigator agrees to allow the Monitor to inspect the drug storage area, drug stocks, drug accountability records, patient charts and study source documents, and other records relative to study conduct.

### **14.4. Retention of Records**

Essential documents should be retained for the period of time required by applicable local law. The essential documents include the signed and dated final protocol, signed and dated amendments(s), if applicable, signed and dated curricula vitae of the Investigators, copies of the completed CRFs, signed ICFs, IEC/IRB approval and all related correspondence, financial agreements, regulatory approval, drug accountability, study correspondence, and patient identification codes. Records will not be destroyed without informing the Sponsor in writing and giving the Sponsor the opportunity to store the records for a longer period of time at the Sponsor's expense.

The ICH requires that patient identification codes be retained for at least 15 years after the completion or discontinuation of the study.

## **15. PUBLICATION POLICY**

Following completion of the study, the data may be considered for publication in a scientific journal or for reporting at a scientific meeting. A copy of the manuscript must be provided and confirmed received at the Sponsor at least 30 days before its submission.

No submission of a manuscript may be made until the results from all of the clinical sites have been received and analyzed by the Sponsor, or the study has been terminated at all centers. A separate, individual publication of the results of the study will be delayed until initial publication of the results of the multicenter study, or a decision not to publish is made. If an initial draft is not produced within 18 months of completion of the study at all centers, or the timeframe for publication is not satisfactory, the Investigator may disclose the results after providing a copy and the Sponsor confirms receipt of the manuscript 30 days before submission.

Research ancillary to this main protocol may not be performed by individual sites without prior discussion and approval by the Sponsor.

## 17. APPENDICES

### Appendix 1: Karnofsky Scale

Able to carry on normal activity and to work; no special care needed.	100	Normal no complaints; no evidence of disease.
	90	Able to carry on normal activity; minor signs or symptoms of disease.
	80	Normal activity with effort; some signs or symptoms of disease.
Unable to work; able to live at home and care for most personal needs; varying amount of assistance needed.	70	Cares for self; unable to carry on normal activity or to do active work.
	60	Requires occasional assistance, but is able to care for most of his personal needs.
	50	Requires considerable assistance and frequent medical care.
Unable to care for self; requires equivalent of institutional or hospital care; disease may be progressing rapidly.	40	Disabled; requires special care and assistance.
	30	Severely disabled; hospital admission is indicated although death not imminent.
	20	Very sick; hospital admission necessary; active supportive treatment necessary.
	10	Moribund; fatal processes progressing rapidly.
	0	Dead

## Appendix 2: New York Heart Association Classification of Heart Failure

Class	Symptomatology
I	No symptoms. Ordinary physical activity such as walking and climbing stairs does not cause fatigue or dyspnea.
II	Symptoms with ordinary physical activity. Walking or climbing stairs rapidly, walking uphill, walking or stair climbing after meals, in cold weather, in wind or when under emotional stress causes undue fatigue or dyspnea.
III	Symptoms with less than ordinary physical activity. Walking one to two blocks on the level and climbing more than one flight of stairs in normal conditions causes undue fatigue or dyspnea.
IV	Symptoms at rest. Inability to carry on any physical activity without fatigue or dyspnea.

### Appendix 3: Categorization of Infusion-Related Reactions

Signs and symptoms of an infusion-related reaction (IRR) usually develop during or shortly after drug infusion and generally resolve completely within 24 hours of completion of infusion.

Signs/symptoms may include: allergic reaction/hypersensitivity (including drug fever), arthralgia (joint pain), bronchospasm, cough, dizziness, dyspnea (shortness of breath), fatigue (asthenia, lethargy, malaise), headache, hypertension, hypotension, myalgia (muscle pain), nausea, pruritus/itching, rash/desquamation, rigors/chills, sweating (diaphoresis), tachycardia, urticaria (hives, welts, wheals), vomiting.

Categorization of IRRs is as follows:

Categorization	Description
Mild	Mild reaction: infusion may be continued; if intervention is indicated it is minimal and additional treatment (other than paracetamol for delayed reactions) is not required.
Moderate	Moderate reaction: requires treatment including more intensive therapy (eg, IV fluids, nonsteroidal anti-inflammatory drug [NSAIDs]) in addition to infusion interruption but responds promptly to medication. Treatment is indicated for $\leq 24$ hours.
Severe	More than moderate reaction: not rapidly responsive to medication or to interruption of infusion; and/ or prolonged (treatment is indicated for $>24$ hours); recurrence of severe symptoms following initial improvement.

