## 6.4.2. Study Drug Administration

Patisiran will be administered under the supervision of the site personnel every 21 ( $\pm$ 3) days. Patients who have received at least 3 doses of patisiran on this study at the clinical site with no evidence of IRRs or other adverse effects may have patisiran administered at home, where applicable country and local regulations allow. Home administration of patisiran will be done by a healthcare professional trained on the protocol and delivery of premedications and patisiran.

On all dosing days, patisiran will be administered as a 70-minute IV infusion (approximately 1 mL/minute for the first 15 minutes followed by approximately 3 mL/minute for the remainder of the infusion).

- If the patient experiences an IRR the infusion time may be extended up to 3 hours in the event of a mild or moderate IRR.
  - 1) If the patient experiences a mild or moderate IRR that resolves by slowing the infusion rate then no further premedication changes are recommended.
  - 2) If the patient experiences a severe IRR, then patisiran administration will not be resumed until the case is discussed with the Medical Monitor (see Section 6.4.3).
- If the infusion time for a patient was already extended on the parent study due to an IRR, that modified infusion duration may be continued on this study for that particular patient. Returning the patient's infusion duration to 70 minutes will require a discussion with the Medical Monitor.
- For the first 3 infusions of patisiran on this study, the patient's infusion site should be assessed for signs of any localized reaction during the infusion and for 30 minutes after the end of the infusion, and the patient will remain at the clinical site for 1 hour following completion of dosing.

If a patient does not receive a dose of patisiran within the dosing window ( $\pm$ 3 days), the dose will be considered missed and not administered.

Additional details can be found in the patisiran Pharmacy Manual.

In addition to study treatment, patients will receive the recommended daily allowance of vitamin A. Patients will receive this daily dose for the duration of their participation in the study while being administered patisiran. In Japan the clinical sites will provide the subjects with a prescription for vitamin A.

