## 6.4.3. Suggested Guidelines for Management of Infusion-Related Reactions

Criteria for categorizing IRRs are provided in [Appendix 3](#).

- In the event of an IRR, the infusion of patisiran may be stopped and the patient closely monitored until resolution of the reaction. Drugs that may be used to facilitate resolution and permit resumption of patisiran administration include, but are not limited to: paracetamol/acetaminophen (or equivalent), additional histamine H1/H2 receptor antagonists (eg, ranitidine), NSAIDs, adrenaline, supplemental oxygen, IV fluids, and/or corticosteroids.
- Following resolution of a mild or moderate IRR that required interruption of the patisiran infusion, resumption of administration may occur at the Investigator's discretion at a slower

infusion rate (but not to exceed 3 hours) for that dose and for all subsequent doses of patisiran. If the infusion is delayed, the administration of the infusion should be completed no more than 6 hours from the initial start of the infusion.

- Patisiran administration will not be resumed for any patient following a severe IRR until the case is discussed with the Medical Monitor.
- If after consultation with the Medical Monitor it is agreed that an individual patient's steroid premedication will be increased then the following steps are **recommended**:
  - 1) If the IRR occurred while the patient received 10 mg intravenous dexamethasone or equivalent at least 60 minutes before the infusion and did not resolve with slowing of the infusion rate, then the patient should be increased by multiples of 5 mg intravenous dexamethasone or equivalent at least 60 minutes before the infusion and/or 5 mg oral dexamethasone or equivalent the night before the intravenous infusion.
  - 2) Increased dose of premedication steroids should NOT exceed the combination of 20 mg intravenous dexamethasone or equivalent on the day of infusion and 8 mg oral dexamethasone or equivalent taken the night before the infusion.
  - 3) If the IRR occurred while the patient received less than 10 mg intravenous dexamethasone or equivalent, then the patient should return to the prior dose of intravenous dexamethasone or equivalent that did not result in an IRR.

Patients will be instructed to call the Investigator if they experience symptoms such as fever, chills, myalgia, or nausea/vomiting after discharge from the site.

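### A serious infusion-related reaction that responds promptly can be graded Moderate under Appendix 3, which leaves same-day resumption to the Investigator without the Medical Monitor discussion

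*Protocol*

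**What the plan says.** Section 6.4.2, item 2 under the IRR bullet: "If the patient experiences a severe IRR, then patisiran administration will not be resumed until the case is discussed with the Medical Monitor". It refers to Section 6.4.3, which repeats the rule: "Patisiran administration will not be resumed for any patient following a severe IRR until the case is discussed with the Medical Monitor". Section 6.4.3 begins by sending the reader to Appendix 3 for the criteria that categorize IRRs.

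Appendix 3 lists possible signs and symptoms, among them hypersensitivity, bronchospasm, dyspnea and hypotension, and ties none of them to a grade. Moderate is a reaction that needs more intensive therapy "in addition to infusion interruption but responds promptly to medication", with treatment indicated for no more than 24 hours. Severe begins "More than moderate reaction: not rapidly responsive to medication or to interruption of infusion" and goes on to prolonged reactions (treatment beyond 24 hours) and to severe symptoms that recur after initial improvement.

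For the lower grades Section 6.4.3 says: "Following resolution of a mild or moderate IRR that required interruption of the patisiran infusion, resumption of administration may occur at the Investigator's discretion". The rate must be slower, and if the infusion is delayed, "the administration of the infusion should be completed no more than 6 hours from the initial start of the infusion". No contact with the Medical Monitor is required on this route.

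The same Appendix 3 wording stands in every protocol version in the file; section references here follow version 3.1 (United Kingdom).

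**The concern.** The Medical Monitor discussion exists so that re-exposure after a bad reaction does not rest on one investigator's judgement. The grade decides whether it applies, and the listed content of the top grade describes how quickly the reaction yields, how long it is treated and whether it returns. It does not describe how dangerous the reaction was. A reaction can be dangerous and still reverse quickly with treatment.

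At stake is re-exposure, within hours, to the drug that has just caused a serious reaction, without the second opinion that the protocol requires after a Severe IRR. Patients who had placebo in the parent study matter most here. Under Section 1.3 they receive open-label patisiran in this study, so inclusion criterion 1 (that the patient tolerated study drug in the parent study) says nothing about whether they tolerate patisiran.

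**Working it through.** No formula applies, and the plan states no figure to reproduce. The check sets the rules side by side and follows one case through them.

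**Test case.** Bronchospasm during the infusion. The infusion is stopped, the reaction is treated and reverses promptly, treatment is indicated for less than 24 hours, and symptoms do not return.

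**Step 1: grade under Appendix 3.**

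| Content listed after the opening phrase of Severe | Met? |
|---|---|
| Not rapidly responsive to medication or interruption | No |
| Prolonged: treatment beyond 24 hours | No |
| Severe symptoms recurring after improvement | No |

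None of the 3 is met. The Moderate description (more intensive therapy, interruption, prompt response, treatment for up to 24 hours) fits throughout. The third Severe item presupposes that symptoms can be severe in themselves, yet it counts only their recurrence; a single severe episode that improves is not listed.

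**Step 2: consequence under 6.4.3.** Read as Moderate, the reaction falls under the discretionary resumption bullet. Completion within 6 hours of the initial start means the same day. The hold in 6.4.2 and 6.4.3 is not triggered.

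**Step 3: the protocol's own view of such an event.** Section 9.2.1.2 gives allergic bronchospasm as an example of an important medical event. The same reaction can thus be a serious adverse event (SAE) and a Moderate IRR.

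**Step 4: which serious criteria a promptly resolving IRR could meet.** Section 9.2.1.2 has 6. Death and congenital anomaly cannot apply to a patient whose infusion is to be resumed, and persistent disability hardly fits prompt resolution. That leaves 6 − 3 = 3: life-threatening, hospitalization (a patient may be admitted for observation after a reaction that settled quickly), and important medical event.

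**Step 5: other safeguards in the document.**

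- Section 9.4 defines a severe adverse event as an incapacitating one, and Section 9.2.1.1 has every IRR recorded as an adverse event. The test case might be severe on that scale. But 6.4.3 points to Appendix 3 for IRRs, so one event can carry two different grades, and only the Appendix 3 grade is clearly linked to the hold.
- Section 9.5.1 requires SAE reports to the CRO immediately and always within 24 hours. That limit is longer than the 6-hour infusion limit, and reporting does not stop a restart.
- Section 4.3 requires contact with the Sponsor before a patient is discontinued after a serious event, not before the infusion is resumed.

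None of the three clearly prevents resumption in the test case.

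**The case against.** The strongest reply is that Severe does open with a general criterion. A reaction that threatens life is, on an ordinary reading, more than moderate, and the therapies that Appendix 3 gives as examples for Moderate are IV fluids and NSAIDs. Section 6.4.2 says only that the IRR is severe, without naming Appendix 3, so an investigator who has graded the event severe under 9.4 has textual grounds to apply the hold. This stands. It makes the defect an ambiguity that permits the wrong route, not a rule that imposes it.

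There are also mitigations. All patients are premedicated. For the first 3 infusions the infusion site is assessed and the patient stays at the clinical site for 1 hour afterwards. Home dosing requires at least 3 site doses without IRRs or other adverse effects. First re-exposures would therefore take place under site staff. Resumption is optional, comes only after resolution, and is at a slower rate. These points reduce the risk but do not add the Medical Monitor discussion.

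A reader might go further and infer from 6.4.3 that resumption without the hold is foreseen even after adrenaline, because "Drugs that may be used to facilitate resolution and permit resumption of patisiran administration include, but are not limited to" is followed by a list that ends with "NSAIDs, adrenaline, supplemental oxygen, IV fluids, and/or corticosteroids". The text does not support that. The bullet applies to an IRR of any grade, and a Severe IRR may also be resumed once the Medical Monitor has discussed it. The list is not evidence either way.

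Finally, seriousness is itself judged by the Investigator, so the remedy does not remove judgement. It does tie that judgement to how dangerous the event was.

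**Conclusion.** The point holds as a gap in a stated safety rule. Appendix 3 has no express criterion for a life-threatening or otherwise serious reaction. An IRR that meets a serious criterion but responds promptly can be read as Moderate, and 6.4.3 then allows same-day resumption without Medical Monitor discussion. Upgrading the grade, or relying on the 9.4 grade, is open to the investigator but not required.

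It would be too strong to say that the protocol grades such reactions as Moderate or directs re-infusion; it does neither. Harm needs an investigator both to read the grade literally and to choose to restart.

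The size cannot be given in patients, because the document states no IRR rate. The conclusion rests on this document alone: the Pharmacy Manual, to which 6.4.2 defers for further detail, and the Investigator's Brochure are not shown and might close the gap. The change is worth making because it is small and concerns patient safety.

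**What to change.** Replace the hold in Section 6.4.2, item 2, and in the third bullet of Section 6.4.3 with one common sentence:

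> After any IRR that is Severe under Appendix 3, or that meets any serious criterion in Section 9.2.1.2, patisiran is not restarted until the case has been discussed with the Medical Monitor.

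In the second bullet of 6.4.3, limit discretionary resumption to mild or moderate IRRs that meet no serious criterion in Section 9.2.1.2. Refer to all the serious criteria, not only to life-threatening and important medical events; otherwise a reaction that settles quickly but leads to admission would be missed. The Appendix 3 grades can stay as they are.

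The drafting cost is one sentence used twice and one limiting clause. In operation it means a few more Medical Monitor calls. Some doses will be delayed, left incomplete or missed when the discussion cannot be held within the 6-hour limit.
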